Children and young adults will be eligible to participate if they are enrolled in the school, have a formal diagnosis of autism, report no use of micronutrient supplements within the last 3 months, are willing to hold other treatments constant for the 8-week study period, have no major medical problems other than ASD, are willing to provide urine samples, and parents were willing to complete on-line surveys at specified intervals. ASD is defined as being present if the child has a diagnosis from a medical professional trained to diagnose autism, or if the student is determined by school staff and the study psychiatrist to meet *Diagnostic and Statistical Manual of Mental Disorders*, Fourth Edition (*DSM-IV*) criteria for ASD. Informed consent will be obtained from the parent/caregiver of all child study participants and directly from all adult study participants. Adults who are conservated will go through an informed consent process and provide assent, and their conservator will be asked to provide informed consent.

Intervention:

The planned study is open-label and all clinicians, parents, and teachers will be aware of the treatment initiation and duration of 8 weeks. All enrolled children will be provided a micronutrient supplementation (EM Power Plus).

Objectives and outcomes:

The primary goal of the study is to determine if any observed changes in symptoms of ASD are correlated with changes in metabolites that occur during treatment with micronutrients. We hypothesize that micronutrient treatment will lead to changes in physiological pathways and that those changes will correlate with clinical improvements.

The two primary outcome measure is the correlation of the changes in clinical symptoms with the change in specific metabolites. Two measures will be used to assess the change in core and associated features of autism: the Autism Behavior Inventory, Short Form (ABI-S) and the Social Responsiveness Scale (SRS). The ABI-S is an observer-reported outcome scale designed specifically to measure change and severity of ASD symptoms and has been shown to have content validity when completed by caregivers.¹¹ The SRS is one of the most commonly used outcome measures in clinical trials of ASD and focuses on social responsiveness and interaction.¹² Parents/caregivers will be asked to complete both measures at baseline, 4 weeks, and 8 weeks using an on-line and secure platform.

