by automated comparison of ion features to a reference library of chemical standards followed by visual inspection for quality control ¹⁴. For statistical analyses and data display, any missing values will be assumed to be below the limits of detection; these values will be imputed with the compound minimum (minimum value imputation). Data will then be normalized by measured osmolality, which is necessary to reduce the variability ¹⁵. A metabolic pathway for a given metabolite will be assigned based on prior designations in the literature combined with experience from prior datasets at Metabolon.

Statistical methods:

Summary statistics will be used to describe the variables. Change in both the clinical variables and the metabolites will be computed as post-test minus pre-test. Pearson's correlation coefficient will be estimated and tested to index the association between the change in each of the two clinical scales and the change in each metabolite. Given the early-stage nature of the research, we will not adjust for multiple comparisons because we believe it was more important to risk a Type II error than to miss a potentially important signal by being overly conservative, as has been suggested by prior authors ¹⁶.

We define, *a priori*, that a correlation cutoff of an absolute value of ≥ 0.6 is of potential clinical relevance, because, given our planned sample size of 25, we will have approximately 80% power to detect a correlation of that size and such a correlation accounts for roughly one-third of the variance. Others have suggested that correlations with an absolute value of ≥ 0.6 indicate a moderate or higher correlation ¹⁷ (and are hence of greatest interest in pointing to a mechanism of action).

We also plan to examine the number of participants who have a “clinical response,” defined *a priori* as an improvement of 4 or more points in the ABI-S. We will compare the pre-post changes in the ABI-S and SRS in the responder and non-responder groups using the student's t-test.

Planned Data Tables:

Table 1: Characteristics of Enrolled Participants

Category	Characteristic	Subjects N=15	
		%	N
Gender	Male		
	Female		
Ethnicity	White		
	Asian/Pacific Islander		
	No response		
Age	7-10		
	11-14		
	15-21		
	Mean Age		
Primary diagnosis	Autism Spectrum Disorder		
Comorbidities	Intellectual Disability		
	Language Disorder		
	ADHD		
	Pica		
	Global Development Delay		
	Learning Disability		
	Other		
Current meds	Sertraline		
	Lurasidone		

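### Responders are defined by ABI-S change and then t-tested against non-responders on that same ABI-S change, so the test is circular and its p-value says nothing about the supplement

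*Combined protocol and SAP*

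**What the plan says.** Three statements in the Statistical methods section combine to create the problem.

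- Change is defined once, for every clinical scale: "Change in both the clinical variables and the metabolites will be computed as post-test minus pre-test".
- Response is defined in advance "as an improvement of 4 or more points in the ABI-S".
- The next sentence plans the test: "We will compare the pre-post changes in the ABI-S and SRS in the responder and non-responder groups", by Student's t-test.

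No other definition of response is given. No separate time point is named for grouping and for testing, and the comparison is not labelled as descriptive.

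Two points of design matter for reading the result. Under Intervention, all enrolled children receive the supplement, there is no control group, and "all clinicians, parents, and teachers will be aware of the treatment initiation". Under Objectives and outcomes, both scales come from the same source: "Parents/caregivers will be asked to complete both measures at baseline, 4 weeks, and 8 weeks".

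The planned sample size is 25 (Statistical methods). The Table 1 shell is headed with 15, so both values are used below.

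**The concern.** A t-test between two groups asks whether their means differ by more than chance would produce. Here the groups are made by cutting the ABI-S change at 4 points, and the means compared are those of the same ABI-S change. A difference is therefore built in. A small p-value confirms only that people selected for larger improvement improved more than people selected for smaller improvement.

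The risk is misreading. In a single-arm, open-label study, a very small p-value on one of the two main clinical scales, attached to the word responder, can be taken as evidence of benefit. It would appear just as readily if the supplement did nothing. The quantity the section does set out to examine, the number of responders, has no planned confidence interval.

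**Working it through.** **The plan's own figure.** The plan gives no power or error rate for this test. Its only power statement concerns the correlation analysis and does not bear on this point.

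**Inputs from the documents.** Cut-off of 4 points; change as post minus pre; Student's t-test; n = 25, with n = 15 from the Table 1 shell.

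**Assumptions, because the documents give no values.** ABI-S change is normal with true mean 0 (no effect) and SD 4, 6, 8 or 10; lower scores are better, so a responder has change ≤ −4 (by symmetry the direction does not matter); two-sided significance level 0.05.

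**Step 1: the logic, which needs no assumptions.** Every responder has a change at or beyond the cut and every non-responder falls short of it. Whenever both groups exist, the responder mean must show more improvement than the non-responder mean.

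**Step 2: the expected gap with no effect.** Let c = 4/SD, let φ be the standard normal density, and let p = Φ(−c) be the expected share of responders. The truncated-normal means are:

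- responders: −SD × φ(c)/p
- non-responders: +SD × φ(c)/(1 − p)
- gap: SD × φ(c)/[p(1 − p)]

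For SD 4: c = 1, φ = 0.2420, p = 0.1587. Responders: −4 × 0.2420/0.1587 = −6.1. Non-responders: 4 × 0.2420/0.8413 = +1.2. The gap is 7.3 after rounding.

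| SD | Responders | Non-responders | Gap |
|---|---|---|---|
| 4 | −6.1 | +1.2 | 7.3 |
| 6 | −7.6 | +2.6 | 10.2 |
| 8 | −9.1 | +4.1 | 13.2 |
| 10 | −10.7 | +5.6 | 16.3 |

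**Step 3: how often the test rejects with no effect.** Simulation of 40,000 trials per setting, pooled two-sample t-test:

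| n | SD | Trials with ≥ 2 per group | Rejection, ≥ 2 per group | Rejection, group of one allowed |
|---|---|---|---|---|
| 25 | 4 | 92.4% | 99.8% | 96.9% |
| 25 | 6 | 99.3% | 99.95% | 99.7% |
| 25 | 8 | 99.9% | 99.98% | 99.95% |
| 25 | 10 | 99.97% | 99.99% | 99.98% |
| 15 | 4 | 71.1% | 97.5% | 86.7% |
| 15 | 6 | 92.1% | 98.7% | 95.5% |
| 15 | 8 | 97.1% | 99.3% | 98.1% |
| 15 | 10 | 98.5% | 99.6% | 99.0% |

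A valid test would reject in 5%. Separate re-runs agree within simulation error (99.7% to 99.99% at n = 25 with at least two per group). With a true mean improvement of 4 points, rejection at n = 25 was 100%, so the result does not separate an active supplement from an inert one. Rounding change to whole points leaves the n = 25 result at 99.9% or above.

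**Step 4: the other reading, paired tests within each group.** These are distorted by the same cut. With no effect and at least two in the group, rejection was:

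| n | Responders | Non-responders |
|---|---|---|
| 25 | 87% to 99% | 32% to 93% |
| 15 | 71% to 87% | 17% to 65% |

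Non-responders nearly always appear to worsen, because removing everyone who improved by 4 or more leaves a positive mean. That direction holds for a true mean change of zero; with real improvement the cut still biases the non-responder mean away from improvement.

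**Step 5: the SRS half of the sentence.** SRS change does not define the groups. When it is unrelated to ABI-S change, its t-test rejects in about 5% of trials, as it should. With an assumed correlation of 0.5 between the two changes and no mean effect, it rejects in about 35% to 50% at n = 25 (SD 3 to 10). It therefore measures agreement between the scales.

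**The case against.** The strongest reply is that little rests on this p-value. The primary outcome is the metabolite correlation, the responder analysis is introduced as an addition, none of the three table shells has a place for it, and whole-sample change is covered in Table 3 with confidence intervals. All of this is true. It limits the damage but does not make the test valid.

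A second reply is that the rejection rates depend on an SD the documents do not give. At smaller SDs many trials would have too few responders to test. Counting all null trials, with groups of one allowed, rejection at n = 25 is about 96% at SD 4, 81% at SD 3 and 40% at SD 2; at n = 15 it is about 80%, 58% and 24%. So the claim of near-certain significance holds among trials where the test can be run, not among all trials at every SD. It does not rescue the test: at SD 2 and 3 it still rejects in 97% to 100% of trials with at least two per group, and in 77% to 90% when a group of one is allowed.

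Grouping at 4 weeks and testing at 8 weeks would break the exact identity, but the documents do not say this. Even then, null rejection is about 80% if the two changes correlate at 0.7 (assumed; n = 25, SD 6).

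Two smaller points stand. That one individual completes both scales for a given child is an inference; the plan says only that parents or caregivers complete both. And a confidence interval for the responder proportion, though useful, does not show a treatment effect in a single-arm, open-label study.

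**Conclusion.** The concern holds. As written, the ABI-S comparison by responder group is circular, and this follows from the definitions alone. The numerical size rests on normal changes, zero true mean change, two-sided 0.05 and an assumed SD of 4 to 10 points. On those assumptions the expected gap is 7.3 to 16.3 points, and among trials with at least two per group the test rejects in 99.7% or more at n = 25 and 97.5% or more at n = 15.

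The fault is confined to the ABI-S half of one sentence. The Pearson correlations on continuous change, the responder count and the SRS comparison are not affected by it. It should be fixed because the p-value is uninformative and easily mistaken for evidence of benefit, but it does not threaten the main analysis.

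**What to change.** - Remove the ABI-S from the t-test sentence, leaving the SRS as the only scale compared between responder groups.
- Show ABI-S change by responder group descriptively, without p-values.
- Report the number and proportion of responders with an exact (Clopper-Pearson) 95% confidence interval. For illustration, 8 of 25 is 32%, with interval 14.9% to 53.5%. State that, without a control group, this does not estimate a treatment effect.
- Label the SRS comparison as agreement between two scales rated by caregivers who know the treatment, not as evidence of benefit.
- No metabolite comparison by responder group is needed to replace the deleted test; the planned correlations on continuous change already address that question.

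The removal is a wording change to one sentence of the Statistical methods, and the reporting and labelling points need a line or two more. No extra data, visits or participants are needed, and the only loss is a p-value that carries no information.

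### The secondary SRS comparison cuts ABI-S change at 4 points before a t-test, discarding about a third to a half of the information if 20–80% respond; a correlation would keep it

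*Combined protocol and SAP*

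**What the plan says.** All of this is in the combined protocol and SAP, under Statistical methods.

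- Both clinical changes are numeric differences: "Change in both the clinical variables and the metabolites will be computed as post-test minus pre-test".
- Where change is related to change, the plan uses Pearson's correlation, but only for "the association between the change in each of the two clinical scales and the change in each metabolite". It calls "a correlation cutoff of an absolute value of ≥ 0.6 is of potential clinical relevance".
- As an additional analysis, it counts responders, meaning those with an "improvement of 4 or more points in the ABI-S", and adds: "We will compare the pre-post changes in the ABI-S and SRS in the responder and non-responder groups using the student's t-test".

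The plan gives no alpha level, power, expected response rate or expected ABI-S/SRS correlation for this comparison. The table shells do not include it either. Table 2 sets each scale beside each metabolite, and Table 3 reports mean scores and mean changes for the two scales separately.

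**The concern.** This point is about the SRS half of the sentence. The ABI-S half, where the groups are defined by the same change that is then tested, is a separate matter.

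Comparing SRS change between ABI-S responders and non-responders asks whether the two changes go together. Both are scores on the same participants, so the question can be put without any cut. With the cut, improvements of 3 and 5 points count as opposites, and improvements of 5 and 20 points count as the same. The group sizes are whatever the 4-point line happens to produce.

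At stake is how the two clinical scales are read together. Mean changes on each scale, as in Table 3, cannot show whether the same participants improved on both. The responder t-test is the only planned analysis that bears on this directly, and it uses the data inefficiently in a small sample. A non-significant result based on a handful of responders would say little about whether the scales move together.

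**Working it through.** **Inputs from the documents.** N = 25 (Statistical methods); the 4-point cut on ABI-S change; the benchmark |r| = 0.6, which was set for metabolite correlations and not for ABI-S against SRS; N = 15 from the Table 1 shell, used only as a sensitivity value.

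**Assumptions, because the documents are silent.** Two-sided alpha of 0.05; bivariate normal changes; true ABI-S/SRS correlation ρ from 0.4 to 0.8; response rates of 10–80% for information and 18–54% for power. The 18% and 54% are the placebo and treated response rates that the Background quotes from an ADHD trial using a clinical global impression scale. They serve only as a plausible range.

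**Step 1. The plan's own power figure.** The plan says "given our planned sample size of 25, we will have approximately 80% power to detect a correlation of that size", meaning 0.6. By Fisher's z, power = Φ(atanh(0.6)·√22 − 1.96) = Φ(3.251 − 1.960) = Φ(1.291) = 90%, and simulation of the Pearson test gives 91%. The stated 80% is therefore not reproduced at two-sided 5%. It belongs to the metabolite correlations, so it is not a power figure for this comparison. The 91% is the reference for an uncut analysis at ρ = 0.6.

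**Step 2. Information kept after the cut.** If a normal variable is cut so that a share p lies above the cut c, the squared correlation with the other variable is multiplied by φ(c)²/[p(1 − p)].

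| Share responding | Calculation | Kept | Lost | 25 acts like |
|---|---|---|---|---|
| 50% | 0.3989²/0.25 | 0.637 | 36% | 15.9 |
| 30% (or 70%) | 0.3477²/0.21 | 0.576 | 42% | 14.4 |
| 20% (or 80%) | 0.2800²/0.16 | 0.490 | 51% | 12.2 |
| 10% (or 90%) | as above | 0.342 | 66% | 8.6 |

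This loss does not depend on ρ. It is smallest, at 36%, when half respond. At 50% responders a true correlation of 0.6 is attenuated to 0.6·√0.637 = 0.48.

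**Step 3. Power.** Simulated data sets were analysed by the Pearson test and by the pooled t-test on responder status. A data set with fewer than two in a group counted as not significant. Repeat runs differ by about one percentage point.

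| ρ (N = 25) | Pearson | t-test, 18% respond | 35% | 54% |
|---|---|---|---|---|
| 0.4 | 53% | 26% | 34% | 35% |
| 0.5 | 75% | 38% | 50–51% | 53% |
| 0.6 | 91% | 54% | 69% | 72–73% |
| 0.8 | nearly 100% | 83% | 96% | 98% |

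Relative loss of power:
- ρ = 0.5: (75 − 53)/75 = 29% to (75 − 38)/75 = 49%.
- ρ = 0.6: (91 − 73)/91 = 20% to (91 − 54)/91 = 41%.
- ρ = 0.8: about 2% to 17%.

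**Step 4. Sensitivity.** With N = 15 and ρ = 0.6, power is 70% for Pearson against 30%, 44% and 47% for the t-test. With 10% responders and N = 25, about 27% of data sets have fewer than two responders.

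**The case against.** The best defence is that this is an additional analysis with no stated power and no table shell, and that nothing primary rests on it. The metabolite correlations keep both clinical changes continuous. A responder contrast fixed in advance is a familiar descriptive device that clinicians read easily. All of that stands, and it limits the weight of the point. It does not justify keeping the contrast as the formal test, because the responder count can be reported without it.

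Four stronger readings are tempting, and the documents do not support them.

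- A reader might infer that the cut costs a third to a half of the *power*. That range describes information. Power loss depends on ρ and the response rate, neither of which is stated. It comes near that range at ρ of about 0.4 to 0.5, is about 20–41% at 0.6, and is small when the scales agree strongly.
- A reader might take 18% and 54% as expected response rates here. They come from another disorder and another scale.
- A reader might infer that the plan intends this test as a check that the two scales agree. It states no such aim and attaches no conclusion to the result. That the test is the only direct link between the scales follows from what is and is not listed.
- A reader might infer that the t-test will usually miss real agreement. At ρ = 0.8 its power is 83–98% over the assumed response rates. The shortfall is serious only for moderate or weak association, or for very uneven groups.

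**Conclusion.** The point holds as a minor one. The SRS comparison cuts a numeric change in two when an uncut analysis, by a method the plan already uses, is available on the same data. If 20–80% respond, about a third to a half of the information is lost (36% at an even split, 51% at 20% or 80%), and more at the extremes.

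In power terms, with N = 25, the cost at an assumed ρ of 0.6 is about 18 to 37 percentage points (91% against 73% down to 54%). At ρ of 0.8 it is about 2 to 17 points. These figures rest on normal changes, two-sided 5% testing and the assumed response rates of 18–54%. The direction of the result does not depend on the exact rate, since no cut of a normal variable loses less than about 36% of the information. The primary analysis is unaffected.

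**What to change.** In Statistical methods, replace the SRS part of the responder t-test with text along these lines:

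> The association between SRS change and ABI-S change will be estimated by Pearson's correlation with a 95% confidence interval and displayed in a scatter plot with the 4-point ABI-S threshold marked. The number of responders, and if wanted the mean SRS change in each group, will be reported descriptively without a test.

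The interval also guards against over-reading a non-significant result. For an observed r of 0.6 with N = 25, it is tanh(0.693 ± 1.96/√22) = tanh(0.275) to tanh(1.111), or about 0.27 to 0.80, which shows how imprecise the estimate is.

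The cost is one sentence and one figure. No new data are needed, and one test replaces another, so the number of tests does not grow in a plan that says "we will not adjust for multiple comparisons". The only loss is that the familiar responder contrast is no longer a formal test.

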Dried blood spots (DBS) will be collected on the day of study initiation and on the final day of the study after the 8-week treatment period. We will be using “batch enrollment” where the parents and caregivers of all potentially eligible participants will be screened for eligibility and asked to go through an informed consent process. Once the final “set” of eligible student participants is identified, they will all be given the study medication and have the DBS sample collected on the same day. DBS is collected using a simple, sterile, finger-prick device and technique, which generates a drop of blood. The participant will be assisted to place his/her finger on a special DBS “card” which will collect the drop of blood. DBS cards will be individually packaged and stored immediately at -80 °C. During the screening visit, children will have a brief physical examination including height and weight to guide the proper dosing. Micronutrient treatment will be provided at the screening visit along with dosing instructions, but participants will not begin the treatment until the study initiation day, when the DBS samples are collected.

Safety assessments:

Parents/caregivers and teachers will be advised to report any concerns about a new medical problem immediately to the study investigators, who will be available at all times to receive reports of possible adverse effects. At the 4 week and 8-week on-line questionnaires, parents/caregivers will be asked to report any new medical problems or concerns for possible side effects.

Metabolomic analyses:

All DBS samples will be sent on dry ice in one batch to Metabolon (Morrisville, NC). Metabolomics analyses will be conducted at Metabolon as previously described ¹³. Briefly, samples will be subjected to methanol extraction, then split into five aliquots for analysis by ultrahigh performance/mass spectrometry in the positive (two methods), negative or polar ion modes. Metabolites will be identified

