	Risperidone		
	Birth Control		
	Zonisamide		
	Other		

Table 2: Metabolite correlations

Metabolite	Primary Outcome Measure				Metabolic Pathway
	ABI-S Corr.	p-value	SRS Corr.	p-value	
Amino acids (endogenous)					
Benzene metabolism					
Cholesterol metabolism					
Fatty acids					
Monoterpene phenol					
Neurotransmitters					
Oxidative stress					
Polyol					
Sphingomyelin					
Sugars					
TCA cycle					
Other					

Table 3. Change in outcome scores over the 12-week study period

Outcome Measure	Adjusted Mean Scores (95% CI)			Change from Baseline (95% CI)			
	Baseline	1 month	3 months	1 month	p	3 months	p
Autism Behavior Inventory Total Score							
Social Communication							
Restrictive and Repetitive Behaviors							
Mental Health							
Self-regulation							
Challenging Behaviors							
Social Responsiveness Scale Total Score							
Awareness							
Cognition							
Communication							
Mannerisms							
Motivation							

Mean change scores will be adjusted for age and gender; *indicates statistically significant change from baseline

REFERENCES:

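### Does the 12-week, three-month labelling of planned Table 3 leave the final tests of symptom change without data?

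*Combined protocol and SAP*

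**What the plan says.** Planned Data Tables, Table 3, is titled "Change in outcome scores over the 12-week study period". It shows adjusted mean scores at baseline, one month and three months, and change from baseline with a p-value at one month and at three months. The rows are the ABI-S total with five subscales and the SRS total with five subscales. The footnote adds: "Mean change scores will be adjusted for age and gender".

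The Methods give eight weeks in five places:

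- Participants: families must be "willing to hold other treatments constant for the 8-week study period".
- Intervention: clinicians, parents and teachers are "aware of the treatment initiation and duration of 8 weeks".
- Objectives and outcomes, clinical scales: caregivers "complete both measures at baseline, 4 weeks, and 8 weeks".
- Objectives and outcomes, dried blood spots: the second sample is taken "on the final day of the study after the 8-week treatment period".
- Safety assessments: new medical problems are asked about "At the 4 week and 8-week on-line questionnaires".

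Statistical methods defines change without naming a week: "Change in both the clinical variables and the metabolites will be computed as post-test minus pre-test".

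**The concern.** The section on statistical methods covers the correlations, the responder count and the comparison of responders with non-responders. It does not describe the age- and gender-adjusted tests of change from baseline. Those appear only in Table 3 and its footnote, so the column headings are the only statement of when the tests are made. If the headings are taken at face value, half of the p-values in the table refer to a time at which nothing is collected, and the score at the end of treatment is not tabulated.

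The trial is open-label with a single arm, and this table is its main planned display of symptom change. A wrong label carried into a report would present an eight-week result as a three-month one. If someone instead took the heading as an instruction to collect a later score, that score would fall four weeks after the end of the treatment period described in the Methods and would have no matching blood sample.

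**Working it through.** No calculation in the plan is at issue, so the check sets the time statements side by side.

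**Inputs.** From Table 3: a 12-week period, with columns at baseline, one month and three months. From the Methods: an 8-week study period, scores at baseline, 4 and 8 weeks, and a final study day after 8 weeks.

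**Can rounding explain it?** At 30.4375 days per month:

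- 4 weeks = 28 / 30.4375 = 0.92 months, which fits the one-month column.
- 8 weeks = 56 / 30.4375 = 1.84 months, which does not fit three months.
- 12 weeks = 84 / 30.4375 = 2.76 months, which fits three months loosely, in line with the table's own title.

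Rounding does not account for the label. The title and the column headings agree with each other, so garbled text extraction does not account for it either.

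**Size of the gap.** 12 − 8 = 4 weeks between the label and the last scheduled score. The table's title sets its period at 12 weeks, so 4 weeks is the figure to use.

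**How many statements conflict directly?** Three of the five: the study period in the eligibility criteria, the scale schedule, and the final study day. Treatment duration and the safety questionnaires are supporting context, since on their own they could sit inside a longer study.

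**How much of the table is affected?** There are 6 ABI-S rows + 6 SRS rows = 12 rows. At two test times that makes 12 × 2 = 24 p-values, of which 12 stand under the three-month heading.

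**Can an analyst fill the column wrongly?**

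| Position | Scheduled score | Table 3 column |
|---|---|---|
| First | baseline | baseline |
| Second | 4 weeks | one month |
| Third | 8 weeks | three months |

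There are three scores for three columns, and the first two pairs match. No score is scheduled after week 8, so the third column can hold only the week-8 score.

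**Does it reach the primary analysis?** The primary outcome is the correlation of symptom change with metabolite change, reported in Table 2. Blood spots are taken on the first day and on the final day after eight weeks, so the metabolite change is fixed to that interval. The clinical change covering the same interval is baseline to week 8. Table 3 plays no part in it.

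**The case for a change.** The strongest case for acting is that the contradiction is in current text and can be verified in minutes. It concerns the timing of tests specified nowhere else, and would cost only a few words to remove. The definition of change as post-test minus pre-test does not settle the timing of the Table 3 tests, because it names no week. Table 3 also reports a score at the middle time point, so post-test alone does not describe it.

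Most of this stands as description. The label is wrong relative to the Methods, and it should not appear in a report as it is. What does not follow is any consequence for the trial. The sections that tell staff what to collect and when are consistent with one another, so the same scores and samples are obtained whether or not the heading is corrected. The tests under the last heading do have data once the column is matched to the only score available. A dataset with time points at baseline, 4 weeks and 8 weeks would show the mismatch to anyone filling in the shell.

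**Conclusion.** The inconsistency is real and clerical. One title and two column headings in an empty table shell are 4 weeks later than the last scheduled score. The Table 3 headings and the assessment schedule need to be reconciled before results are reported, but that is copy-editing. It does not change what is collected, which comparisons are made, or what the trial can conclude. It introduces no bias, and the primary correlation, its power and the sample size are untouched.

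This rests on one assumption: that no 12-week assessment is intended. The documents do not say how the label arose, so a mislabelled column is an inference. It is a strong one, because the Methods place the final day of the study after the eight-week treatment period and mention no follow-up or extension. If a later assessment were in fact planned, the Methods would be missing a visit and the point would need to be reopened. No view is taken here on how long treatment should last.
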